#### **5.5.7.2.** Biopsy

Sensitivity and PPV are defined from imaging results in subjects undergoing a biopsy confirmed by conventional imaging and histology obtained from this biopsy. This will be performed for Cohort B only.

Criteria for Positive PyL Imaging Result	Criteria for Biopsy and Positive Histology
Biopsied Lesion consistent with PSMA Positive uptake on the  F-DCFPyL PET/CT = yes	Pathology result=Positive for prostate cancer

If Cohort =B, imaging and histology are obtained for the biopsy, and the above criteria are not met (Biopsied Lesion consistent with PSMA Positive uptake on the F-DCFPyL PET/CT = no or pathology result = negative) then results = Negative for each respective endpoint.

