12.3. Endpoints and Derivations

12.3.1. Sensitivity, Specificity, PPV, and NPV

Table 7 will be used to classify the combined pelvic lymph node packets (left or right) from Cohort A and biopsy from Cohort B according to its ¹⁸F-DCFPyL image result (positive or negative) generated from central imaging review and its histopathology result (positive or negative for prostate cancer) generated by the sites' pathology review. Nodes identified on ¹⁸F-DCFPyL PET/CT images in areas that were not removed in surgery for Cohort A will not be tabulated due to absence of histopathology.

Table 7: Classification of ¹⁸F-DCFPyL Imaging Result and Histopathology Result for Cohorts A and B Separately

	Histopatho	ology Result	
¹⁸ F-DCFPyL Image	Positive*	Negative	
Positive	ТР	FP	I(p)
Negative	FN	TN	I(n)
	R(p)	R(n)	Nı

TP=true positive; FP=false positive; FN=false negative; TN=true negative.

R(p) and R(n) denote the subjects with a positive or negative lobe or biopsy, respectively, based on histopathology. I(p) and I(n) denote the subjects with a positive and negative lesion, respectively, based on the ¹⁸F-DCFPyL image. N_1 indicates the number of subjects with evaluable pelvic lymph node packets from Cohort A or the number of subjects with evaluable biopsies from Cohort B.

*Positive histopathology should be for prostate cancer only.

The following statistics will be computed:

- Sensitivity = TP/R(p),
- Specificity = TN/R(n),
- Positive predictive value (PPV) = TP/I(p),
- Negative predictive value (NPV) = TN/I(n).

For Cohort A, a true positive or true negative must be determined from imaging and histopathology aligning on outcome overall.

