#### 3.1.2. Secondary Objectives

- 1. To evaluate the safety and tolerability of F-DCFPyL
- 2. To assess the diagnostic performance of F-DCFPyL PET/CT imaging to determine the presence or absence of prostate cancer within sites of metastasis or local recurrence (cohort B).
- 3. To determine detection rates of F-DCFPyL PET/CT and conventional imaging among lesion locations (e.g., bone, lymph nodes, soft tissue, prostate gland)
- 4. To determine positive and negative predictive value (PPV and NPV) of F-DCFPyL PET/CT imaging
- 5. To determine the pharmacokinetics, bio-distribution and excretion of F-DCFPyL

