### 5.5.7. Sensitivity, Specificity, PPV, and NPV

Sensitivity, specificity, PPV and NPV will be defined based on a F-DCFPyL image result (positive or negative) and a histopathology result (positive or negative).

Table 3: Classification of F-DCFPyL Imaging Result and Histopathology Result

	Histopatho		
 F-DCFPyL Image Positive* Negative			
Positive	TP	FP	I(p)
Negative	Negative FN		I(n)
	R(p)	R(n)	N

TP=true positive; FP=false positive; FN=false negative; TN=true negative.

The following statistics will be computed:

- Sensitivity = TP/R(p),
- Specificity = TN/R(n),
- Positive predictive value (PPV) = TP/I(p),
- Negative predictive value (NPV) = TN/I(n).

R(p) and R(n) denote the number of subjects with positive and negative histopathology results, respectively.

I(p) and I(n) denote the number of subjects with positive and negative F-DCFPyL images, respectively.

N indicates the number of subjects

\*positive histology should be for prostate cancer only

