#### 7.7.2. PPV and Sensitivity in Cohort B

Point estimates and two-sided 95% CIs for PPV and Sensitivity will be computed from the conventional guided biopsy obtained from subjects in Cohort B for the Evaluable Set. The normal approximation to the binomial distribution is planned assuming a null hypothesis of 0.5. If the assumptions are not met, then confidence intervals derived from an Agresti-Coull exact test will be used (See Section 7.2). Results will be computed for each of the three central imaging core lab independent readers.

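### The Cohort B objective covers absence as well as presence of cancer, but only sensitivity and PPV are estimated, and the 0.50 reference is weak in a disease-enriched biopsy sample

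*SAP*

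**What the plan says.** The second secondary objective (Protocol 4.2, SAP 3.1.2) is to assess diagnostic performance to "determine the presence or absence of prostate cancer within sites of metastasis or local recurrence (cohort B").

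The Cohort B accuracy endpoints are sensitivity and PPV only (Protocol 5.2 items 2 and 5; SAP 3.2.2 items 1 and 5). The analyses match. Protocol 12.5.2.2 lists those two for Cohort B and counts each as successful if the lower 95% limit is above 0.50 for at least two of the three readers. SAP 5.5.7.2 states "Sensitivity and PPV are defined from imaging results in subjects undergoing a biopsy", and SAP 7.7.2 states "Point estimates and two-sided 95% CIs for PPV and Sensitivity will be computed from the conventional guided biopsy", with a null value of 0.5 and Agresti-Coull limits if the normal approximation fails. SAP 7.7.2 does not repeat the two-of-three rule.

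The classification is nevertheless complete. Protocol Table 7 is titled for the imaging result and "Histopathology Result for Cohorts A and B Separately"; it has a true-negative cell, and all four accuracy formulas stand beneath it. SAP Table 3 keeps the same cells and formulas. SAP 5.5.7.2 says when a Cohort B image, and when a biopsy, is coded negative.

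Two rules shape the sample. Cohort B entry requires disease visible on imaging (Protocol 7.1, criterion 6), and the preferred biopsy targets are lesions that look suspicious on most modalities (Protocol 10.4). SAP 4.1 goes further and describes Cohort B subjects as biopsied when the PET/CT showed a positive lesion.

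**The concern.** Sensitivity uses only the cancer-positive biopsies, and PPV only the image-positive ones. PPV does count false positives, but neither statistic credits a correct negative. The half of the objective that concerns absence therefore has no matching estimate.

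In a sample selected to contain cancer, PPV is high before the scan is read. For a reader who calls everything positive, sensitivity is 1 by construction and PPV equals the share of biopsies with cancer. A reference of 0.50 asks whether that share clearly exceeds one half, not whether the scan added anything to the selection for biopsy. At stake is a secondary claim: a pass on both statistics could be reported as diagnostic performance when it mostly reflects who was biopsied.

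**Working it through.** **Plan's own figure.** The documents give no Cohort B calculation. The only powered figure is for Cohort A, and it reproduces. The SAP 4.3 formula with P0 = 0.40, P1 = 0.60, two-sided 0.05 and 80% power gives n = 47.09; 47.09/0.20 = 235.5, so 236 evaluable; 236/0.9 = 262.2, stated as 262. For specificity (0.80 against 0.878), n = 184.5 and 184.5/0.80 = 230.6, so sensitivity drives the size.

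**Inputs for Cohort B.**
- About 115 dosed (Protocol 12.1, SAP 4.3). The evaluable number is not stated. I assume 104, which is 115 × 0.9 = 103.5 using Cohort A's 10% loss, and also show other sizes.
- Reference 0.50, two-sided 95% limits, at least two of three readers (Protocol 12.5.2.2).
- Share of biopsies with cancer, π: not stated, so a range is used.

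**All-positive reader.** FN = TN = 0, so TP = R(p), FP = R(n) and I(p) = N.

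*Sensitivity* = R(p)/R(p) = 1. The normal approximation fails, so Agresti-Coull applies. At 52/52, n' = 52 + 3.84 = 55.84, p' = (52 + 1.92)/55.84 = 0.966, and the lower limit is 0.966 − 1.96·√(0.966·0.034/55.84) = 0.92. For 58 to 115 evaluable and π from 0.40 to 0.90 the lower limit runs from 0.83 to 0.96. It always exceeds 0.50.

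*PPV* = R(p)/N. The lower limit is p − 1.96·√(p(1−p)/N). With N = 104, 62 positives (59.6%) give 0.502 and pass; 61 (58.7%) give 0.492 and fail. Minimum counts to pass:

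| Evaluable | Positive biopsies needed | Share |
|---|---|---|
| 115 | 68 | 59.1% |
| 104 | 62 | 59.6% |
| 80 | 49 | 61.3% |
| 58 | 37 | 63.8% |

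The chance of passing PPV is P(X ≥ 62) for X binomial(104, π):

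| π | 0.50 | 0.55 | 0.60 | 0.65 | 0.70 | 0.75 or more |
|---|---|---|---|---|---|---|
| Chance | 3% | 20% | 57% | 89% | 99% | about 100% |

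If all three readers call everything positive, their tables are identical, so the two-of-three rule changes nothing. Simulated readers who call 90% positive regardless of histology pass both statistics with probability 0.51 at π = 0.60, 0.86 at 0.65 and 0.99 at 0.70.

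**What specificity would add.** With 104 evaluable and π = 0.70, 0.80 or 0.90 there are about 31, 21 or 10 negative biopsies. At a true specificity of 0.80 the half-width 1.96·√(0.16/n) is 0.14, 0.17 or 0.25. These are normal-approximation figures. With 21 and 10 negatives, n(1−p) is 4.2 and 2, so SAP 7.2.1 would switch to Agresti-Coull. The all-positive reader scores 0 out of R(n). For 0/21, n' = 24.84, p' = 1.92/24.84 = 0.077, and the upper limit is 0.18. His NPV is 0/0 and cannot be computed. Even few negatives expose an uninformative read.

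**The case against.** The case for the plan is substantial, and much of it stands.

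- **PPV penalises false positives.** A reader might infer that calling everything positive guarantees success in Cohort B. It does not. Below about 60% positivity that reader usually fails PPV, and the documents give no positivity rate.
- **Estimates are reported, not only a pass or fail.** A reader might infer that a good scan and an empty one would give the same results. They would not. With an assumed sensitivity of 0.90 and specificity of 0.80, PPV at π = 0.60 is 0.54/(0.54 + 0.08) = 0.87, against 0.60 for the all-positive reader; at π = 0.70 it is 0.63/(0.63 + 0.06) = 0.91, against 0.70. But these can be told apart only if the biopsy-positive rate is shown beside PPV, and SAP 7.7.2 does not ask for that.
- **The SAP did not drop an endpoint.** A reader might infer from Table 7 that SAP section 10 omits a change. Protocol 5.2 and 12.5.2.2 name only sensitivity and PPV for Cohort B, so the SAP follows the protocol. Protocol 12.3.1 is a shared definitions section.
- **The data are not discarded.** Negative images and biopsies are coded, and listing 16.2.6-1 and tables 14.2.3-11 and 14.2.3-12 are planned. What is missing is an estimate.
- **The consequence is limited.** Cohort B is secondary and unpowered. The efficacy conclusion rests on Cohort A, where the lower specificity limit must exceed 0.80 for at least two readers.
- **Specificity here would be imprecise and selected.** True. That is a reason to label it so, not to omit it when the objective asks about absence.

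**Conclusion.** The point holds as a mismatch between objective and endpoint in both documents: Cohort B is meant to address presence and absence, and no planned estimate addresses absence. The 0.50 reference adds little protection. An all-positive read always passes sensitivity, and passes PPV once about 60% of biopsies are positive (59% to 64% for 115 down to 58 evaluable).

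The size depends on two unstated quantities: the evaluable number, taken as 104, and the biopsy-positive rate. Entry and lesion selection make a rate above 60% plausible, but that remains an assumption. The documents do not support saying that an uninformative read necessarily succeeds, or that the SAP made an undeclared change. The primary conclusion of the trial is untouched.

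**What to change.** In SAP 5.5.7.2, SAP 7.7.2 and Table 14.2.2-1:

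1. Report the Cohort B two-by-two table per reader, with specificity and NPV and 95% intervals, using Agresti-Coull where SAP 7.2.1 requires it. State how NPV is shown when a reader has no negative calls.
2. Present PPV beside the biopsy-positive rate in the same subjects, and say that exceeding 0.50 is not by itself evidence of diagnostic performance.
3. Label specificity and NPV as descriptive, imprecise (half-width about 0.14 to 0.25 with 31 to 10 negatives at a true specificity of 0.80) and based on selected negatives.
4. Reconcile the SAP 4.1 description of biopsy as dependent on a positive PET/CT with the biopsy selection in the protocol. Selection on PET would leave few image-negative biopsies, pushing sensitivity up and specificity down.

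The alternative to items 1 and 3 is to narrow the Cohort B objective to detection of disease in both documents.

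No new success criterion should be added. A threshold on the positive likelihood ratio, for example, would be unpowered and undefined when there are no false positives.

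The cost is SAP wording and a few table rows, using data already coded. The drawback is wide intervals and possibly a less favourable-looking Cohort B result.

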#### 5.5.7.3. Prostate Gland

Sensitivity, specificity, PPV and NPV will be calculated from imaging and histology results from the prostate gland. This will be performed for subjects in Cohort A only.

Criteria for Positive PyL Imaging Result	Criteria for Positive Histology
For category = PYL and Prostate gland right lesion count $\geq 1$ or Prostate gland left lesion count $\geq 1$	If Prostate gland right lesion count ≥0 from imaging and Adenocarcinoma is present at right side of prostate or
	Prostate gland left lesion count ≥0 from imaging and Adenocarcinoma is present at left side of prostate

If Cohort = A and Adenocarcinoma results are not missing for the right or left side of the prostate and the above criteria is not met, then result = Negative.

If imaging results are both not evaluable or the presence of adenocarcinoma is missing from both the left and right side of the prostate then this endpoint is missing.

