7. SELECTION AND WITHDRAWAL OF SUBJECTS

7.1. Subject Inclusion Criteria

Subjects must meet all of the following inclusion criteria:

All Cohorts:

- 1. Adults ≥ 18 years of age.
- 2. Subjects provide signed informed consent and confirm that they are able and willing to comply with all protocol requirements.
- 3. Histologically confirmed adenocarcinoma of the prostate.

Cohort A Only:

- 4. At least high risk prostate cancer defined by NCCN Guidelines Version 3.2016 (clinical stage \geq T3a or PSA >20 ng/mL or Gleason score \geq 8).⁴⁷
- 5. Scheduled or will be scheduled to undergo radical prostatectomy with PLND.

Cohort B Only:

- 6. Radiologic evidence of local recurrence or new or progressive metastatic disease demonstrated on anatomical imaging (CT, MRI, or ultrasound), whole-body bone scan (^{99m}Tc-MDP or Na¹⁸F) within 4 weeks of Day 1.
- 7. If prior treatment with radiation or ablative therapy, evidence of recurrence outside the confines of prior treated site(s).
- 8. Scheduled or will be scheduled for percutaneous biopsy of at least one amenable lesion.

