7.2. Subject Exclusion Criteria

Subjects meeting any of the following exclusion criteria are not eligible for this study:

All Cohorts:

- 9. Subjects administered any high energy (>300 KeV) gamma-emitting radioisotope within five physical half-lives, or any IV iodinated contrast medium within 24 hours, or any high density oral contrast medium (oral water contrast is acceptable) within 5 days, prior to study drug injection.
- 10. Subjects with any medical condition or other circumstances that, in the opinion of the investigator, compromise obtaining reliable data, achieving study objectives, or completion.

Cohort A Only:

11. Patients with prior androgen deprivation therapy or any investigational neoadjuvant agent or intervention

Cohort B Only:

- 12. Prior radiation or ablative therapy to intended site of biopsy, if within the prostate bed.
- 13. Initiation of new systemic therapy for recurrent and/or progressive metastatic disease since radiographic documentation of recurrence/progression.

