10.5. Biopsy and Surgical Pathology

Immediately following biopsy or surgery, the specimens will be sent for histopathological processing and analysis at the site in accordance with the study Pathology Manual.

Gross handling of the prostate gland and lymphadenectomy specimens, if applicable, will include whole gland assessment and sectioning of the entire prostate gland, overall measurement of specimen size, lesion location, dissection and description (including location) of identified lymph nodes, and submission of lymph nodes in their entirety plus all remaining fibroadipose tissue for each harvested regional packet. Histopathology results of the prostate gland and pelvic lymph nodes (Cohort A) or biopsy location (Cohort B) will be recorded in the eCRF.

Should a Cohort A subject forego RP surgery and undergo alternative procedure for prostate cancer (e.g., biopsy), the procedure and corresponding histopathology data will be recorded in the eCRF. Likewise, should a Cohort B subject receive additional procedure for prostate cancer, the procedure and corresponding histopathology data will be recorded in the eCRF.

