## 7.2. Testing Statistical Assumptions Including Comparability at Baseline

#### 7.2.1. Test of Proportions

The assumption underlying the normal approximation to the binomial distribution, used in the computation of confidence intervals for sensitivity, specificity, PPV, and NPV, is that the sample size is such that np>5 and n(1-p)>5, where n is the sample size and p is the binomial probability. It is expected that the sample size for each statistic will be sufficient to meet this assumption. In the event that the sample size is not sufficient, Agresti-Coull exact tests will be used. As there is only one treatment in this study, there will be no testing of baseline comparability.

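### Subject-level prostate gland specificity in Cohort A rests on few or no gland-negative men, and gland PPV cannot move far from prevalence

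*SAP*

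**What the plan says.** **Who is in Cohort A.** Protocol 7.1 requires, for all cohorts, "Histologically confirmed adenocarcinoma of the prostate". Cohort A men are scheduled for radical prostatectomy. Protocol 7.2 excludes from Cohort A "Patients with prior androgen deprivation therapy or any investigational neoadjuvant agent or intervention". Prior radiation or ablation is not expressly excluded for Cohort A; the exclusion that mentions it applies to Cohort B only. Protocol 10.5 calls for "whole gland assessment and sectioning of the entire prostate gland".

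**How the gland is scored.** SAP 5.5.7.3 opens with "Sensitivity, specificity, PPV and NPV will be calculated from imaging and histology results from the prostate gland". Imaging is positive if either side has at least one lesion. Histology is positive if adenocarcinoma is present on a side whose imaging lesion count is zero or more, on the right or the left. The result is negative if "Adenocarcinoma results are not missing for the right or left side of the prostate and the above criteria is not met". SAP 5.5.7 fixes the unit of counting: "R(p) and R(n) denote the number of subjects with positive and negative histopathology results, respectively". Specificity is TN/R(n), PPV is TP/I(p) and NPV is TN/I(n).

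**Where the results are used.** Gland PPV and NPV are secondary (Protocol 5.2 item 4; SAP 3.2.2 and 7.7.1). Gland sensitivity and specificity are exploratory, with a null of 0.5 (SAP 3.2.3 and 7.8). Protocol 12.5.2.2, however, lists Cohort A PPV and NPV for the pelvic node packets only.

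**What is said about small numbers.** SAP 7.2.1 requires np>5 and n(1-p)>5 for the normal approximation. It adds "It is expected that the sample size for each statistic will be sufficient to meet this assumption" and then "In the event that the sample size is not sufficient, Agresti-Coull exact tests will be used".

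**The concern.** A specificity estimate needs subjects without the target condition, and this cohort is selected for having it. The either-side rule removes the one natural source of negatives: a man with cancer on one side is simply positive, and his cancer-free side is never counted. The few negatives that remain may not all be cancer-free. If the cancer-bearing side is not evaluable on imaging and the other side is clear, the lesion-count condition is not met and the man is scored histology-negative. The same happens if one side's histology is missing and the other side is benign. The documents do not say how often either would occur.

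At stake is what the gland rows can tell a reader. A PPV near 100% would look like strong performance although an uninformative scan would score almost the same. A specificity based on a handful of men would be set against a null that it may have no chance of rejecting. The SAP gives no rule for R(n)=0.

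**Working it through.** **The plan's own sizing (nodes only).** Protocol 12.1 and SAP 4.3: two-sided alpha 0.05, power 80%, nodal prevalence 20%, 10% non-evaluable.

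- Sensitivity 0.40 vs 0.60: n = {[1.960×√0.24 + 0.8416×√0.24]/0.20}² = 47.09; 47.09/0.20 = 235.5, so 236.
- Specificity 0.80 vs 0.878: n = 184.5; 184.5/0.80 = 230.6, below 236.
- 236/0.90 = 262.2, stated as 262.

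The figures reproduce. They concern the pelvic nodes; neither document gives a prevalence or an expected number of negatives for the gland.

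**How many gland-negatives.** Let f be the gland-negative share (an assumption) and take N = 236 as a stand-in. Expected R(n) = N×f and P(R(n)=0) = (1−f)^N.

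| f | Expected R(n) | P(R(n)=0): specificity undefined |
|---|---|---|
| 0 | 0 | 100% |
| 0.5% | 1.2 | 31% |
| 1% | 2.4 | 9% |
| 2% | 4.7 | 0.8% |
| 5% | 11.8 | about 0 |

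**PPV.** TP = Se×(N−R(n)) and FP = (1−Sp)×R(n). An uninformative scan (Se+Sp=1) has PPV equal to prevalence, (N−R(n))/N. Assumed Se 0.80 to 0.95, Sp 0.5 to 0.9.

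- R(n)=7, Se 0.80, Sp 0.5: 183.2/(183.2+3.5) = 98.1%. Uninformative: 229/236 = 97.0%.
- R(n)=1, Se 0.95, Sp 0.9: 223.25/(223.25+0.1) = 99.96%. Uninformative: 235/236 = 99.6%.
- R(n)=12 (5%): 179.2/185.2 = 96.8% up to 212.8/214.0 = 99.4%. Uninformative: 224/236 = 94.9%.

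**NPV.** TN/(TN+FN), with TN = Sp×R(n) and FN = (1−Se)×(N−R(n)).

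- R(n)=1, Se 0.80, Sp 0.5: 0.5/47.5 = 1%.
- R(n)=7, Se 0.80, Sp 0.5: 3.5/49.3 = 7%.
- R(n)=7, Se 0.95, Sp 0.9: 6.3/17.75 = 35%.

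NPV is low, but it does respond to the tracer.

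**Specificity against 0.5.** Agresti-Coull 95% limits: p̃ = (x+z²/2)/(n+z²), then p̃ ± z√[p̃(1−p̃)/(n+z²)], z = 1.96, upper limit capped at 1.

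| Correct/R(n) | Lower | Upper |
|---|---|---|
| 2/2 | 0.29 | 1 |
| 4/4 | 0.454 | 1 |
| 5/5 | 0.511 | 1 |
| 6/7 | 0.467 | 0.995 |
| 7/7 | 0.596 | 1 |
| 10/12 | 0.54 | below 1 |

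With R(n) of 4 or fewer, no result puts the lower limit above 0.5. With 5 to 7, only a perfect score does; at R(n)=7 and true specificity 0.90 that has probability 0.90⁷ = 0.48. At R(n)=12, 10 correct suffices, with probability 0.89 at true specificity 0.90 and 0.56 at 0.80.

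**Normal approximation.** Requiring np>5 and n(1−p)>5 takes at least 11 negatives at p=0.5 (11/236 = 4.7%) and 26 at p=0.8 (26/236 = 11.0%).

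**The case against.** The strongest reply is that little depends on these rows. Gland specificity is exploratory, gland PPV and NPV are secondary, SAP 7.7.1 attaches no null to Cohort A PPV and NPV, and none of them enters the success rule in SAP 7.6.1. A reader who sees the counts beside a wide interval would not be misled. The SAP also provides Agresti-Coull for small samples, and one result per subject matches the unit used for the nodes.

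The point about consequence stands and limits the weight of the finding. The fallback does not answer it: Agresti-Coull changes the interval method, but adds no gland-negative men and cannot define 0/0.

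Three stronger readings are tempting, and the documents do not support them.

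- *The 0.5 null cannot be tested.* That holds only at R(n) of 4 or fewer. At 12 it is testable, and the documents do not say which case applies. Because prior radiation or ablation is not expressly excluded for Cohort A, some true negatives are possible.
- *PPV is near 100% whatever the tracer does.* That fails for a reader worse than chance: at R(n)=12 with Se=Sp=0.20, PPV is 44.8/(44.8+9.6) = 82%.
- *More than 10 negatives secure the normal approximation.* That is the minimum at p=0.5; a higher specificity needs more.

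It is also fair to object that a side-level analysis may not rescue PPV. If only 24 of 472 sides are negative, prevalence is the same as with 12 of 236 men, and so is PPV: 96.8 to 99.4% against 94.9% for an uninformative scan.

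**Conclusion.** The concern holds in this form. The entry criteria and the either-side, subject-level rule leave few or no gland-negative men, so gland specificity is undefined or very imprecise, and gland PPV for any reader no worse than chance lies between prevalence and 1. Over the assumed 0.5 to 3% range, PPV differs from that of an uninformative scan by at most about 3 percentage points (the width of 97.0 to 100% at R(n)=7).

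The scarcity follows from the documents. The numbers rest on an assumed gland-negative share, on 236 as the denominator, and on assumed sensitivity and specificity; the problem eases as the share approaches 5%. Gland sensitivity, the nodal co-primary endpoints and the success rule are not touched, and nothing here supports an inference about them. The change should be made because it is cheap; the primary conclusion does not depend on it.

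**What to change.** **In SAP 5.5.7.3, 7.7.1 and 7.8, add a side-level gland analysis.** Classify left and right separately. Imaging is positive if that side's lesion count is 1 or more and negative if 0. Histology follows adenocarcinoma present or absent on that side. Exclude a side with non-evaluable imaging or missing histology. Report sensitivity, specificity, PPV and NPV per reader, with prevalence and the number of negative sides. Intervals must allow for two sides per man: a subject-level cluster bootstrap or, at 0% or 100%, Agresti-Coull on a cluster-adjusted effective sample size or on the number of subjects.

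**At subject level,** keep gland sensitivity as a detection rate. Present gland specificity, PPV and NPV as descriptive, show R(n), report specificity as not estimable if R(n)=0, and drop the 0.5 null for specificity.

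**Housekeeping.** Record the change in SAP Section 10, and reconcile Protocol 5.2 item 4 (gland and nodes) with Protocol 12.5.2.2 (node packets only).

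**Cost.** No new data: SAP 5.5.7.3 and 5.5.8 already name the side-level fields. It needs a SAP amendment and modest programming.

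**Limits.** Specificity gains negatives only as far as disease is one-sided, a share the documents do not give. If 10 to 40% of 236 men had one clear side (assumption), there would be about 24 to 94 negative sides. At specificity 0.80 the Agresti-Coull interval, ignoring clustering, would run from 60–92% (24 sides) to 71–87% (94 sides). Uninformative PPV would be 448/472 = 95% to 378/472 = 80%, so side-level PPV stays partly prevalence-driven and at the low end is no better than the subject-level figure.
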